**Table 1 Schedule of Assessments**

Assessments	Visits										Extended Follow-up (if needed)
	Screening (Up to 5 Weeks)	Treatment Period (12 Weeks)						Post-Treatment Follow-up Period (8 Weeks)			
		Baseline 	Day 1 	Day 4 (±1 day)	Day 15 (±2 days)	Day 29 (±3 days)	Day 57 (±3 days)	Day 85 (±3 days)	Day 99 (±3 days)	Day 113 (±3 days)	Day 141 (±3 days) or ET 
Informed consent	X										
Demographics	X										
Medical History	X	X									
Prior/concomitant Medications	X	X		X	X	X	X	X	X	X	
Body weight and height 	X	X		X	X	X			X	X	
Vital Signs 	X	X		X	X	X			X	X	
12-lead ECG 	X										
Complete Physical Examination 	X										
Baseline Diet Assessment 	X										
Baseline Diet Compliance 		X		X	X	X	X	X	X	X	
Stool for Ova and Parasite 	X										
ePRO Activation and Training 	X										
ePRO Questionnaire 	<----- Perform DAILY from Screening through Day 141 or 28 days after last dose if ET ----->										
██████████ 	X	X (pre-dose)			X (pre-dose)	X (pre-dose)	X (pre-dose)		X	X	
EGD with Biopsy 	X								X		
██████████ 	X								X		
Serum Pregnancy test & FSH 	X										
Urine Pregnancy test 		X (pre-dose)			X (pre-dose)	X (pre-dose)	X (pre-dose)			X	
Eligibility Assessment	X	X									
Stratification and Randomization 		X (pre-dose)									
Access IRT-enter PID and subject weight		X (pre-dose)			X (pre-dose)	X (pre-dose)	X (pre-dose)				
Access IRT for first subject screened to trigger first IP shipment	X										

**Table 1** Schedule of Assessments cont.

Assessments	Visits										Extended Follow-up (if needed)
	Screening (Up to 5 Weeks)	Treatment Period (12 Weeks)						Post-Treatment Follow-up Period (8 Weeks)			
Assessments	Baseline 	Day 1 	Day 4 (±1 day)	Day 15 (±2 days)	Day 29 (±3 days)	Day 57 (±3 days)	Day 85 (±3 days)	Day 99 (±3 days)	Day 113 (±3 days)	Day 141 (±3 days) or ET 	Every 28 Days  (±3 days)
Premedication with cetirizine and acetaminophen or approved alternative 		X (pre-dose)			X (pre-dose)	X (pre-dose)	X (pre-dose)				
Study drug administration 		X			X	X	X				
Symptom-directed Physical Exam 		X		X	X	X	X		X	X	
CBC with differential 	X	X	X	X	X	X	X	X	X	X	X

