- 11) To be completed by subject, in clinic, prior to any blood draw, physical exam, or vital sign measurements.
- 12) Specimen processed by central lab. See central laboratory manual for collection and processing details.
- 13) See Protocol Appendix 5 for biopsy assessments. The post-treatment endoscopy (EGD) and biopsy assessments will be performed on Day 99 ( $\pm 3$ ) and biopsy results will be blinded.
- 14) To be performed during the conduct of the EGD during the screening period and on D99.
- 15) Blood for serum pregnancy and FSH will be collected on screening, for subjects of childbearing ability or to show post-menopausal status.
- 16) Urine for urine pregnancy test will be collected pre-dose on all infusion days and at EOS. Test kits will be supplied by the central lab. Tests will be completed on site and evaluated prior to infusion(s).
- 17) Stratification based on highest weekly symptom average recorded (group of 3.0–4.9 or 5.0–10.0). Randomization and stratification will occur through Cenduit IRT.
- 18) Premedication required prior to first and second infusions and at the Investigator's discretion for third and fourth infusions, depending on tolerance of prior infusions.

- 19) Study drug will be administered as a single peripheral IV infusion over at least 5 hours on study Day 1 and at least 4 hours on Day 29 ( $\pm 3$  days) and Day 57 ( $\pm 3$  days). The infusion may be shortened to 3–5 hours for Day 85 ( $\pm 3$  days). Please refer to the Pharmacy Manual for detailed instructions on study drug preparations, administration, and infusion rates. Infusion must be completed within 8 hours of preparation of study drug.
- 20) A symptom-directed PE (including assessment of possible infusion site reactions) will be performed by the Investigator or designee, as needed if any symptoms are reported.

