- 21) Blood for CBC with differential, including absolute [REDACTED] and basophil counts, will be obtained just prior to each infusion, 1 hour after the end of each infusion, 4 hours after the end of infusion 1, as well as during the screening period and on Days 4, 15, 99, 113, and 141 or ET and Extended Follow-Up, if applicable. All differential blood counts from Day 1 (post-dose) and prior to Day 141 or Early Termination will be blinded to the Sponsor and the site. An unscheduled CBC may be collected at the request of the unblinded safety monitor. Differential blood counts will not be blinded at the Day 141/ET visit and these results will be used by the site to determine if the subject needs to enter the Extended Follow-Up period.
- 22) Blood for chemistry will be obtained pre-dose on dosing Days 1, 29, 57, and 85, as well as during the screening period and on Day 15, Day 113, and Day 141 or ET.
- 23) Urine for standard urinalysis will be obtained pre-dose on dosing Days 1, 29, 57, and 85, as well as during the screening period and on Day 113 and Day 141 or ET.
- 24) Serology will include HBsAg, hepatitis C antibody, anti-HBc, and HIV.
- 25) If an Infusion-related reaction causes an infusion interruption or cessation a sample of blood should be obtained for exploratory safety analysis within 1–2 hours of the onset of the symptoms. A sample of blood should be obtained for testing of histamine and tryptase levels within 1–2 hours, if anaphylaxis is suspected.
- 26) Blood for PK should be obtained pre-dose on dosing Days 29, 57, and 85, as well as during screening and on Days 15, 113, and 141 or ET.
- 27) Blood samples for exploratory analysis will be collected pre-dose on Days 1, 29, and 85 and also on Day 141 or ET.
- 28) Blood samples for ADA will be collected during the screening period, on Days 15, 29, 57, 85 and Day 141 or ET and anytime an immunogenicity-related AE occurs.
- 29) Blood samples for Total Serum IgE will be collected on Day 1 and on Day 141 or ET.
- 30) The ET Visit should be conducted 28 ( $\pm 3$ ) days after the last dose of study drug or prior to this, if necessary, to ensure compliance with the visit. If early termination occurs more than 28 days after the last dose of study drug, then perform the ET visit as soon as possible. The procedures listed under the final follow-up visit will be conducted unless directed otherwise by the Medical Monitor.

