### 5.2 Secondary Efficacy Endpoint

#### 1st Secondary Endpoint

Proportion of Treatment Responders, defined as patients with >30% reduction in TSS score combined with a >75% reduction in eosinophils in the gastric and/or duodenal mucosa. The eosinophil count is obtained on Day 99 (Week 14) biopsy and the TSS score for the analysis will be the average of the 14 daily scores starting with the day of the last dose to the day before the end of study biopsy. If a minimum of 7 daily scores are not recorded in this nominal 14-day window, the window will be rolled back until a

minimum of 7 scores are present. For patients whose biopsy is collected prior to Day 99 due to early discontinuation, the average of the last 14 days of TSS scores recorded for that patient will be used for the analysis.

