### 2nd Secondary Endpoint

Percent change from baseline in the TSS scores averaged over the 14 daily scores starting with the day of the last dose to the day before the end of study biopsy. For patients whose biopsy is collected prior to Day 99 due to early discontinuation, the average of the last 14 days of TSS scores recorded for that patient will be used for the analysis. (See 1st Secondary Endpoint for the calculation of TSS average.)

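### For an early biopsy the symptom score uses the last 14 diary days recorded with no cut-off at the biopsy, so it can include or consist of scores recorded after the biopsy it is paired with

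*SAP*

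**What the plan says.** Section 5.2 (1st Secondary Endpoint) and the Treatment Responder entry of Table 2 in Section 4 give two rules for the end-of-treatment TSS.

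- **Standard rule:** "the average of the 14 daily scores starting with the day of the last dose to the day before the end of study biopsy". If fewer than 7 scores lie in that nominal 14-day window, it is rolled back until 7 are present.
- **Early-biopsy rule:** when a subject stops early and is therefore biopsied before Day 99, the SAP substitutes "the average of the last 14 days of TSS scores recorded for that patient will be used for the analysis".

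The 2nd Secondary Endpoint, percent change in TSS "averaged over the 14 daily scores starting with the day of the last dose to the day before the end of study biopsy", carries the same early-biopsy rule. So do the exploratory scores in Section 5.3 and the matching analysis text in Section 7.12.

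Three entries in Table 1 and its notes bear on when those last recorded days fall.

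- The diary row reads "Perform DAILY from Screening through Day 141 or 28 days after last dose if ET".
- Note 30 puts the early-termination (ET) visit at 28 (±3) "days after the last dose of study drug or prior to this, if necessary, to ensure compliance with the visit". It adds: "The procedures listed under the final follow-up visit will be conducted unless directed otherwise by the Medical Monitor".
- Note 13 dates only the planned biopsy: "The post-treatment endoscopy (EGD) and biopsy assessments will be performed on Day 99" (±3). The SAP gives no date for a biopsy taken early.

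**The concern.** The first secondary endpoint needs a symptom response and a histologic response in the same subject. The standard rule keeps the two together by ending the symptom window the day before the biopsy. The early-biopsy rule drops that anchor and takes whatever was recorded last. Where the diary continues beyond the biopsy, the two halves of the responder definition can describe different periods. This does not come from sparse diaries: it arises with a complete diary, and better diary compliance moves the window later.

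The score enters steps 2, 3 and 6 of the testing sequence in Section 6.8, where one failed step makes every later test non-significant. Early discontinuers can be in the efficacy analysis, because the per-protocol example in Section 7.1.2 excludes only those with fewer than 2 doses.

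**Working it through.** No sample size or power figure is involved. The check is a count of days, with day 0 the day of the last dose.

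**Inputs (all SAP):** doses on Days 1, 29, 57 and 85 (Section 3.1); planned biopsy Day 99 ±3 (Table 1, note 13); standard and early-biopsy windows (Section 5.2); diary to 28 days after the last dose if ET (Table 1).

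**1. The plan's own window.** Last dose Day 85 and biopsy Day 99 give Days 85 to 98. That is 98 − 85 + 1 = 14 days, or days 0-13 after the last dose. This reproduces the nominal 14 days.

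**2. The early-biopsy window.** If the diary ends *e* days after the last dose, the last 14 days are *e* − 13 to *e*. The number shared with days 0-13 is max(0, 27 − *e*) for *e* of 14 or more.

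| Diary ends at day *e* | Window (days after last dose) | Days shared with 0-13 |
|---|---|---|
| 14 | 1-14 | 13 |
| 21 | 8-21 | 6 |
| 25 | 12-25 | 2 |
| 28 (as scheduled) | 15-28 | 0 |

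With the diary kept to day 28, the study days are 44-57 for a last dose on Day 29, 72-85 for Day 57, and 100-113 for Day 85.

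**3. Position relative to the biopsy.** For a biopsy *k* days after the last dose and a diary to day 28, the number of the 14 scores on or after the biopsy day is min(14, 29 − *k*).

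| Biopsy at day *k* | Scores on or after the biopsy day |
|---|---|
| 15 or earlier | 14 of 14 |
| 18 | 11 |
| 21 | 8 |
| 24 | 5 |
| 28 | 1 |

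**4. A case needing no assumed biopsy date.** Take a last dose on Day 85, discontinuation, a biopsy before Day 99 for that reason, and the diary kept to day 28. The window is Days 100-113, so all 14 scores follow the biopsy whatever its exact date.

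**5. Scale of one subject.** With 20 per group (Section 3.5), one changed responder moves a single arm by 1/20 = 5 percentage points and the pooled active group by 1/40 = 2.5 points. These are illustrations; the per-protocol groups may be smaller.

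**The case against.** The strongest reply is that the SAP leaves a gap here rather than making a demonstrated error.

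- **The biopsy date is open.** If an early biopsy is done at a day-28 ET visit, 13 of the 14 scores precede it and only one falls on the biopsy day. Pairing is then nearly intact. The protocol was not available for this review and may fix the date. This stands: the mismatch is possible, not certain.
- **The window need not be days 15-28.** The ET visit may be earlier and the rule uses days actually recorded, so a diary that stops sooner gives an earlier window. This also stands.
- **Few subjects are reached.** A subject must discontinue early, be biopsied before Day 99 for that reason, and stay in the per-protocol population. The number could be zero or one. If 5-10% of 60 subjects discontinued, that would be 3-6 people, but the rate is an assumption and the figure would be a ceiling on those reached, not a count of subjects mis-scored.

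A reader might infer that these scores are taken off drug and reflect fading effect. The SAP does not support that. Doses are 28 days apart, so days 15-28 lie within one planned dosing interval. Section 5.3 itself plans efficacy averages over Weeks 9-14, which cover days 15-28 after a Day 57 dose.

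A reader might also infer that a later window relative to dosing is itself an error. The documents do not establish this. The ±3-day visit windows alone let the gap from last dose to biopsy run from 96 − 88 = 8 to 102 − 82 = 20 days, and roll-back moves some windows earlier.

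Contamination by other therapy is limited, though not excluded, by the steroid and prohibited-medication examples in Section 7.1.2.

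What survives is narrower: a rule for a biopsy-paired endpoint sets no limit at the biopsy, while the schedule keeps the diary running.

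**Conclusion.** The point holds as a defect in a stated rule. Followed literally, the early-biopsy rule can pair a biopsy with symptom scores recorded partly or wholly after it. The extent runs from 1 of 14 scores (biopsy at day 28) to all 14 (biopsy within 15 days of the last dose), provided the diary is kept to day 28 as scheduled.

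The SAP gives neither the early-biopsy date nor the number of early discontinuers. The affected number is probably small, and there is no basis for saying which arm would gain; a claim of bias in a particular direction would go beyond the document. The change is worth making because the scores enter gated endpoints with about 20 subjects per arm, and the SAP already uses the missing cut-off in its standard rule.

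**What to change.** Replace the early-biopsy sentence with:

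> *If a subject's biopsy is taken before Day 99 because of early discontinuation, TSS is averaged over the last 14 days of scores recorded before the date of that biopsy. Scores on or after the biopsy date are not used. The 7-score minimum with roll-back applies.*

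Use the same wording in Table 2, in Section 5.2 for both secondary endpoints, and for the exploratory scores in Sections 5.3 and 7.12. Make the change before unblinding.

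The wording refers to recorded scores, not to the 14 calendar days before the biopsy, because a calendar window could be sparse or empty if the diary stops before the biopsy. It repairs the pairing with the biopsy and is not meant to align the window with dosing: for a biopsy at day 28 with a complete diary, the window moves only from days 15-28 to days 14-27.

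The cost is one repeated sentence and no new data. A few subjects may have fewer usable diary days, which the 7-score minimum with roll-back is there to handle.

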### 2nd Secondary Endpoint

Percent change from baseline in the TSS scores averaged over the 14 daily scores starting with the day of the last dose to the day before the end of study biopsy. For patients whose biopsy is collected prior to Day 99 due to early discontinuation, the average of the last 14 days of TSS scores recorded for that patient will be used for the analysis. (See 1st Secondary Endpoint for the calculation of TSS average.)

## 5.3 Exploratory Endpoints

- Change from baseline in the [REDACTED] counts by visit.
- Change from baseline in the [REDACTED] scores averaged over the 14 daily scores starting with the day of the last dose to the day before the end of study biopsy. For patients whose biopsy is collected prior to Day 99 due to early discontinuation, the average of the last 14 days of scores recorded for that patient will be used for the analysis. (See 1st Secondary Endpoint for the calculation of average.)
- Percent change from baseline in the [REDACTED] scores averaged over the 14 daily scores starting with the day of the last dose to the day before the end of study biopsy. For patients whose biopsy is collected prior to Day 99 due to early discontinuation, the average of the last 14 days of [REDACTED] scores recorded for that patient will be used for the analysis. (See 1st Secondary Endpoint for the calculation of [REDACTED] average.)
- Percent Change from baseline to Week 14 (Day 99) in the number of [REDACTED] in patients with [REDACTED].
- Proportion of
  - EG patients with average [REDACTED] per HPF in [REDACTED],
  - EGE patients with average [REDACTED] per HPF in [REDACTED], and
  - EoE patients with average [REDACTED] per HPF in [REDACTED].
- [REDACTED] before and after treatment.
- Change from baseline to Week 14 (Day 99) in the number of [REDACTED] in
  - [REDACTED],
  - [REDACTED]

- Change from baseline in the scoring of [REDACTED] using the [REDACTED].
- Changes from baseline to Week 14 (Day 99) in [REDACTED]
  - [REDACTED]
- Change from baseline in the [REDACTED] for patients with [REDACTED]
- Percent changes from baseline in the [REDACTED] and [REDACTED] for averages of Weeks 13-14, 11-14 and Weeks 9-14 and separately for each individual week.
- Changes from baseline in the [REDACTED] for averages of Weeks 13-14, 11-14 and Weeks 9-14 and separately for each individual week.
- Change from baseline in [REDACTED] over time.
- [REDACTED] at baseline and Day 99.
- Distribution of [REDACTED] in the histological findings at Day 99.

#### 5.4 Pharmacokinetic (PK) Endpoints

- Serum concentrations of AK002 prior to each dose and on Days 15, 113 and 141 (or ET).

#### 5.5 Safety Endpoints

Safety endpoints include:

- Treatment-emergent adverse events (TEAEs)
- Change in laboratory test results (Hematology, Blood chemistry, Urinalysis)
- Changes in vital signs

- Physical examination
- Anti-drug (AK002) antibody (ADA)
- Concomitant medication

## 6. Statistical Methods

### 6.1 General Methodology

All statistical analyses will be conducted using SAS v 9.4 or later version on the Microsoft Windows Operating System.

All CRF data (raw data) will be converted into SDTM (Study Data Tabulation Model) datasets, which will be used to create ADaM (Analysis Data Model) data sets. The creation of the SDTM and ADaM data sets will follow the CDISC (Clinical Data Interchange Standards Consortium) standards and the FDA Study Data Technical Conformance Guide. All analysis tables and listings will be created from the ADaM data sets.

Continuous data will be summarized using n (number of subjects with non-missing observations), mean, median, standard deviation (SD), minimum value, and maximum value. Categorical data will be summarized using the frequency count and percentage (n, %) of subjects in each category. Number of subjects with non-missing values or number of subjects with missing values (e.g., Not Done) will be presented, where appropriate. Subjects with missing values will not contribute to the denominator for percentage calculations, unless specified otherwise. Counts of zero in any category will be presented without percentage. All summaries will be presented for individual treatment groups. In addition, for summary of disposition and subject baseline characteristics, the presentation will include all 3 groups combined. For summary of efficacy and safety endpoints, the presentation will include both active dose groups combined.

The precision rules for the presentation of summary statistics will be:

- Sample size (n, N) and number of missing responses (if displayed) – Integer
- Mean, confidence interval, and median – One more decimal place than reported/collected
- Standard deviation – Two more decimal places than reported/collected
- Percentiles, minimum, maximum – Same number of decimal places as reported/collected
- Ratio – two decimal places
- Percentage – one decimal place generally, or two decimal places for <0.1%

The data summaries will be accompanied by individual subject data listings. All data available from questionnaires, eCRF, and external transfer (labs) will be listed and will include relevant subject information, e.g., treatment group and study day. The listings will be sorted in the order of subject ID, and assessment date/time and assessment name.

For each summary table, a supporting listing will be identified in the footnote.

Dates will be presented in the ISO-8601 format YYYY-MM-DD. Times will be displayed in 24-hour clock format. Numbering for tables, figures and listings will follow ICH E3 Guideline (ICH, 1996).

Alternative methods of analysis of the data may be considered prior to database lock should some of the assumptions underlying the proposed analyses not be met. Reason for departure from the planned methods will be documented as an amendment to the SAP or in the CSR.

## 6.2 Visit Window and Unscheduled Assessments

There is no visit window for the by-visit analysis. Data will be analyzed according to the visit they are associated with, unless specified otherwise.

## 6.3 Adjustment for Covariates

Baseline and randomization stratum may be adjusted, where appropriate, in estimating the between group difference using ANCOVA, MMRM, or Cochran-Mantel-Haenszel tests.

## 6.4 Handling of Dropouts, Missing Data, and Data Discrepancies

For the exploratory endpoints of percent change in the weekly [REDACTED], when  $\geq 3$  of 7 daily scores are available, the weekly average score will be calculated using the available daily scores. This calculation implies the missing daily scores are the same as the mean of the non-missing daily scores. When  $>4$  daily scores are missing, the weekly score will be set to missing. For the weekly [REDACTED], when  $\geq 4$  of 8 weekly [REDACTED] scores are available, [REDACTED] will be calculated using the available weekly [REDACTED] scores. Otherwise, the weekly [REDACTED] will be set to missing. For the [REDACTED] (Section 6.9), when  $\geq 2$  weekly [REDACTED] scores are available, [REDACTED] will be calculated using the available weekly [REDACTED] scores. Otherwise, [REDACTED] will be set to missing.

The exploratory analysis for the [REDACTED] will be based on the [REDACTED] model (Section 6.9). Except for the implicit imputation described above, no imputation will be applied to the missing data. Under the MAR assumption, the [REDACTED] analysis is considered unbiased.

AEs with incomplete start or stop dates (i.e., either day or month is missing) will be considered treatment-emergent (TEAE) unless the partial start date or the stop date confirms the AE started or ended prior to Study Day 1 (e.g., the day of the AE start date is unknown but the month and year indicate that the AE starts prior to Study Day 1). AEs with missing relationship to study drug will be included in the “Related” category for the summary tables. AEs with missing severity will not be included in the by-severity summary table but will be footnoted in the table.

When there is incomplete information regarding dosing dates for prior and concomitant medication, the medication will be considered as a concomitant medication unless it contradicts with the stop date. For example, a medication will be considered a prior medication if the month and year of the end date indicates a date before Study Day 1 even though the start date could be missing.

